#### **18.5 Genetic Testing**

No genetic research will be performed on the samples acquired in this clinical trial.

#### **18.6 Confidentiality**

The medical, hospital and research records associated with this study are considered confidential. Members of the treating team and designated study assistants will have access to the records as required to administer treatment and comply with the protocol. Neither the name nor any other identifying information for an individual will be used for reporting or publication regarding this study. All laboratory and baseline data will be de-identified and transferred via secure links at Weill Cornell Medicine. Patient records will be made available for inspection to auditing agencies to satisfy regulatory requirements.

#### **18.7 Research Conflict of Interest**

[name], who is Co-Principal Investigator on this study, has been paid as a member of the speakers' bureau and advisory board for Bristol Myers Squibb (BMS), and maker of one of the study drugs, Nivolumab.

## APPENDIX 1: Laboratory Correlate Manual

*Please refer to the study lab manual for more information on shipping and handling research specimens.*

**At Baseline** BIOPSIES: >3 core biopsies from the lesion selected to be irradiated is obtained and delivered to [name] lab.  
One core will be assigned for histology, one for RNA/DNA, and one for PDX generation.  
Blood: Six 10 mL lavender top (EDTA) tubes—to WCM Core Lab  
One 10 mL red top (serum) tube—serum to be processed and frozen by WCM Core Lab (Total research blood draw this day 70 mL)

**First 3 ipi infusions:** Blood: Six 10 mL lavender top (EDTA) tubes—to WCM Core Lab  
One 10 mL red top (serum) tube—serum to be processed and frozen by WCM Core Lab (Total research blood draw this day 70 mL)

**Day 22:** Blood: Six 10 mL lavender top (EDTA) tubes—to WCM Core Lab  
One 10 mL red top (serum) tube—serum to be processed and frozen by WCM Core Lab (Total research blood draw this day 70 mL)  
*Optional tissue biopsy will be obtained at Day 22.*

**First 3 Nivo infusions:** Blood: Six 10 mL lavender top (EDTA) tubes—to WCM Core Lab  
One 10 mL red top (serum) tube—serum to be processed and frozen by WCM Core Lab (Total research blood draw this day 70 mL)

**Day 70:** Blood: Three 10 mL lavender top (EDTA) tubes—to WCM core lab  
(*Total research blood draw this day 30 mL*)

**Follow up visit:** (at 6 months from starting treatment):

Blood: Six 10 mL lavender top (EDTA) tubes—to WCM Core Lab  
One 10 mL red top (serum) tube—serum to be processed and frozen by WCM Core Lab (Total research blood draw this day 70 mL)

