Criteria for Evaluation (Efficacy, safety, stopping rules, etc.)	
CLINICAL ENDPOINTS
 
Tumor Response will be evaluated using the RECIST best response (Partial Response (PR) + Complete Response (CR)). The irradiated lesion will be excluded from the assessment of response.
 
Time to progression and duration of response are also endpoints of the study.
 
IMMUNOLOGICAL ENDPOINTS
 
We propose to analyze immunological changes that reflect both local and systemic responses, and investigate both general immune activation as well as tumor antigen-specific T- and B-cell responses. Serial blood samples will be collected for serum and peripheral blood mononuclear cells (PBMC): at baseline (pre-treatment, end of radiation therapy), at the time of the first three infusions of ipilimumab, at the time of the first three infusions of nivolumab, at response evaluation (Day 70 <math>\pm</math> 7 days), and at 6 months. Small aliquots of PBMC (<math>\sim 10^6</math> cells) will be used ex vivo for preparation of DNA and RNA, and the remainder preserved frozen until evaluation by flow cytometry and/or by functional assays. In addition, Stool samples will be collected before treatment, at day 22, at Day 70 response (<math>\pm</math> 7 days) and 6 months to explore changes of the microbiome during ICB. Tissue biopsies will be obtained at baseline and at Day 22 (optional), post treatment from patients who consent to the optional biopsies.

Statistics	
A Simon's two-stage optimal design will be used. The null hypothesis is that the true response rate is 31% will be tested against a one-sided alternative. If there are 4 or fewer responses in these 15 patients, the study will be stopped. Otherwise 29 additional patients will be accrued for a total of 44 patients. The null hypothesis will be rejected if 18 or more responses are observed in 44 patients. This design yields a type I error of 0.10 and power of 90% when the true response rate is 51%. The target sample size is 44 evaluable patients and up to 48 patients will be accrued to account for non-evaluable patients or patients who withdraw prior to the 9-week evaluation.

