### **Experimental methods**

Serial blood for immune monitoring studies will be collected at baseline, end of radiation therapy, at the time of the first three infusions of ipilimumab, at the time of the first three infusions of nivolumab, at response evaluation (day 70), and at 6 month follow up. Small aliquots of PBMC will be used ex vivo for preparation of DNA and RNA, and the remainder preserved frozen until evaluation by flow cytometry and/or by functional assays. Biopsies of the lesion to be irradiated will be obtained at baseline in all patients. Optional post-treatment biopsy will be performed at Day 22 in patients with an accessible, non-irradiated metastasis. We expect approximately 50% of the patients to comply with the second tissue acquisition. The choice of a non-irradiated lesion is motivated by safety concerns, after RT.

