### Experimental methods

Serial serum samples will be used to measure IFN $\square$  and CXCL11 by ELISA. sMICA, sMICB and antibodies anti-sMICA and anti-sMICB will be measured in serum by ELISA using recombinant MICA/B protein and anti-human MICA mAb, in collaboration with [name] (Dana Farber) with whom we have an ongoing collaboration. MICA expression in tumors will be tested by IHC. sMICA/B and anti-sMICA/B antibody levels, and expression levels of NKG2D in circulating CD8 and NK cells will be plotted over time to identify the nature of the changes and summarized using longitudinal mixed effects regression models that incorporate the repeated observations over time (fixed effects) within the same patient (random effect) and missing observations. Baseline levels and changes from baseline at the time of post treatment biopsy will be plotted for each of these markers and correlation coefficients with 95% confidence intervals will be estimated to evaluate the association between the serum and tumor marker levels.

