Changes in the gut microbiome will be assessed globally and at each individual timepoint. In the global analysis of measure of diversity, the data will be summarized by a normalized area under the curve (AUC). The AUC of responders will be compared to the AUC of non-responders using a two-group t-test (or non-parametric test if more appropriate). In addition, logistic regression will assess the relationship of the AUC for the diversity index and responder status. This model may adjust for baseline levels of diversity and other relative clinical variables. Changes in the diversity index will also be evaluated at each timepoint and compared between responders and none responders using a two-group t-test (or non-parametric test if needed). A similar analysis will be done with the changes in serum marker levels over time. A global analysis will be done using a normalized AUC and making a comparison between responders and non-responders. There will also be analyses done for changes at each timepoint between responders and non-responders. For these analysis, we will also generate graphs of the data that show the changes over time in the measurements for each individual patient (i.e. a spaghetti plot). We will superimpose a loess curves on the plot: one for the entire cohort, one for responders and one for non-responders). Given the relatively small sample size, these analyses are exploratory and no adjustment will be made for multiple comparisons.

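### Appendix 1 lists no serum tube at Day 70 and has no end-of-radiation draw, although the synopsis calls for serum at both and the analysis compares serum markers at each time point

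*Combined protocol and SAP*

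**What the plan says.** **Tube list.** At Day 70, Appendix 1 gives "Three 10 mL lavender top (EDTA) tubes—to WCM core lab" and the total "Total research blood draw this day 30 mL". At baseline, the first three ipilimumab infusions, Day 22, the first three nivolumab infusions and 6 months it gives six EDTA tubes plus "One 10 mL red top (serum) tube—serum to be processed and frozen by WCM Core Lab", 70 mL in all. It has no entry for the end of radiation.

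**Where serum is called for.**
- The synopsis, under Immunological Endpoints: "Serial blood samples will be collected for serum and peripheral blood mononuclear cells (PBMC", followed by a list of times that includes the end of radiation and "at response evaluation (Day 70", with a window of 7 days either side.
- Section 4.0, Objective 2.4, Experimental methods: "sMICA, sMICB and antibodies anti-sMICA and anti-sMICB will be measured in serum by ELISA". The same paragraph uses serial serum for the interferon and CXCL11 assays.
- The sub-study (Section 22.0, Approach): blood at baseline, Day 22, Day 70 and 6 months, with lymphocytes and serum separated and frozen.

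**Analysis.** After describing the microbiome comparison, Section 17.3 (Secondary analyses) says: "A similar analysis will be done with the changes in serum marker levels over time". It then specifies a normalized AUC and a comparison of responders with non-responders for the change at each time point.

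**End of radiation.** Section 4.0, Objective 2.3, Experimental methods: "Serial blood for immune monitoring studies will be collected at baseline, end of radiation therapy". The same draw appears in both synopsis lists, in note e of the Section 10.0 calendar and in Section 18.4.

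**The concern.** Appendix 1 is the only tube list in the text available for review. If a site draws what it lists, no serum is taken at the visit where response is assessed, and serum that was never drawn cannot be recovered later. The per-time-point comparison in Section 17.3 would then have nothing to analyse for Day 70.

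The other serum draws between Day 22 and 6 months are tied to infusions, not to calendar visits. Section 6.0 delays both drugs for most Grade 2 or higher non-skin drug-related events and sets out when they must be stopped. Whether a patient has serum near the response visit therefore depends on toxicity. That is an awkward missing-data pattern for a comparison of responders with non-responders, because Section 1.3 itself reports an association between response and severe immune-mediated events in melanoma.

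**Working it through.** **1. Is the missing tube an artefact of the text?** Tubes multiplied by 10 mL:
- Day 70: 3 × 10 = 30 mL, the stated total.
- Every other draw: 6 × 10 + 1 × 10 = 70 mL, the stated total.

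The Day 70 total leaves no room for a serum tube, so none was lost in reading the PDF.

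**2. Nominal serum days.** Section 6.0 gives ipilimumab on Days 1 and 22 and then every 6 weeks, and nivolumab from Day 22 every 3 weeks.
- First three ipilimumab infusions: Days 1, 22 and 22 + 42 = 64.
- First three nivolumab infusions: Days 22, 22 + 21 = 43 and 43 + 21 = 64.

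| Nominal time (baseline and Day 1 counted as one) | Serum in synopsis | Serum tube in Appendix 1 |
|---|---|---|
| Baseline / Day 1 | yes | yes |
| End of radiation (Day 5) | yes | no entry |
| Day 22 | yes | yes |
| Day 43 | yes | yes |
| Day 64 | yes | yes |
| Day 70 | yes | no |
| 6 months | yes | yes |

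Two of the seven nominal times lack a serum tube in Appendix 1.

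**3. Does Day 64 stand in for Day 70?** The response window is 70 ± 7, or Days 63 to 77. The third infusions fall on nominal Day 64, six days before nominal Day 70 and inside that window. With the ± 3 day infusion window in calendar note h, they can fall on Days 61 to 67. A patient dosed on schedule therefore has serum in the response window or at most two days before it (63 − 61 = 2). A patient who is off drug across Days 63 to 77 has none there. One stopped after Day 22 has none from Day 22 until 6 months.

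**4. Effect on the normalized AUC.** Assumptions: the trapezoid rule, which the plan does not specify, and 6 months = Day 180. The weight of an interior point is half the distance between its two neighbours, divided by the total span (180 − 1 = 179 days). The end-of-radiation draw is left out.

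| Patient | Weight with Day 70 serum | Without it |
|---|---|---|
| On schedule (1, 22, 43, 64, 70, 180) | Day 70: (180 − 64)/2/179 = 58/179 = 32%; Day 64: (70 − 43)/2/179 = 13.5/179 = 7.5% | Day 64: (180 − 43)/2/179 = 68.5/179 = 38% |
| Stopped after Day 22 (1, 22, 70, 180) | Day 70: (180 − 22)/2/179 = 79/179 = 44% | Straight line from Day 22 to Day 180; Day 22: (180 − 1)/2/179 = 50% |
| On schedule, series ends at Day 70 | Day 70: (70 − 64)/2/69 = 3/69 = 4% | Series ends at Day 64 |

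For a patient on schedule, most of the lost weight moves to a sample taken six days earlier, so the practical loss is small. For a patient stopped early, nothing near the response visit can take its place.

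**The case against.** Much of the case on the other side stands.

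- **Day 70 is not the objective's key time point.** A reader might infer that the serum objective loses the sample it depends on. The documents do not support that. The only specific change time in the Objective 2.4 methods is the post-treatment biopsy. That is Day 22, when serum is drawn, and the preliminary data behind the objective are also from Day 22. Section 17.3 refers to each time point and does not single out Day 70.
- **The long interval before 6 months is mostly scheduled spacing.** A Day 70 tube shortens it by six days for a patient on schedule. It should not be charged to the missing tube.
- **The loss cannot be put as a count of patients.** It would be wrong to say that every accrued patient would otherwise have Day 70 serum. Up to four of the 48 are accrued to replace patients who withdraw or are not evaluable. The documents also do not say how many will miss or delay the third infusions.
- **Appendix 1 may not be the last word.** Calendar note e and Section 18.3 refer to Appendix 2 for the blood draws, and Appendix 1 mentions a study lab manual. Neither could be seen. Appendix 1 cites the lab manual for shipping and handling, however, and gives the tube list itself.
- **Plasma.** The synopsis, under Correlative Studies, speaks of storing serum/plasma, and EDTA tubes yield plasma. No section allows plasma in the Objective 2.4 assays. Equally, none proposes switching to plasma at one visit, so bias from such a switch is conjecture.
- **The small draw may be deliberate.** It has its own total and comes about six days after a 70 mL draw. In that case it is the synopsis, Section 17.3 and the sub-study that need to change.
- **Limited stakes.** Section 17.3 labels these analyses exploratory. The Objective 2.4 mixed model is said to handle missing observations. It is described for the sMICA/B levels, their antibodies and NKG2D expression, though, and no missing-data handling is stated for the AUC or the per-time-point tests.

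**Conclusion.** The contradiction is real. Appendix 1 draws no serum at Day 70, while the synopsis and the sub-study call for it and Section 17.3 would analyse it. If Appendix 1 is followed as written, the Day 70 serum comparison has no sample. Appendix 1 also gives no tube list for the end-of-radiation draw, which five other places in the protocol require.

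The consequence is modest. One comparison time is lost for all patients. Those dosed on schedule keep a serum sample at about Day 64, and those off drug around the response visit keep none near it, so the gap varies with toxicity. Under the trapezoid rule with 6 months at Day 180, a Day 70 value would carry 32% of the AUC weight on schedule and 44% after stopping at Day 22.

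The primary endpoint, the two-stage decision rule, PFS, OS and the safety analysis are untouched. The conclusion assumes that Appendix 2 and the lab manual, which could not be seen, do not already supply the missing tubes.

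**What to change.** 1. In Appendix 1, add one 10 mL red-top serum tube at Day 70, which takes the draw from 30 to 40 mL.
2. Add an end-of-radiation entry to Appendix 1 with its own tube list, including serum as in the synopsis.
3. Check both entries against Appendix 2 and the study lab manual so that all three agree.

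If the smaller Day 70 draw was intended, state instead that Day 70 is not a serum time point. Amend the synopsis, Section 17.3 and the sub-study's Approach to match. The end-of-radiation entry is needed either way.

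The cost is manual wording, 10 mL more blood at a visit where blood is already drawn, tubes for an end-of-radiation draw that the protocol already requires, and minor processing and storage.

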### Biospy collection:

#### Prior to sample collection

1. Please email [name] – [[contact]](mailto:[contact]) and [name] – [[contact]](mailto:[contact]) once a patient consents with the biopsy schedule.
2. The sub site will alert about a patient enrolment as soon as possible, and at least a week in advance, and communicate the estimated time of arrival (ETA) of patient biopsy to Lab. [Note: The physician consenting the patient should make sure that the radiologist performing the biopsy is aware that this is a research biopsy and that if possible >3 cores **at least 18G are needed**).

#### Patient sample collection

1. Please prepare a 50 ml Falcon Tube filled with 20 ml sterile RPMI-1640 medium supplemented with 10% heat-inactivated fetal bovine serum, 2mM Glutamine, Penicillin 100U/ml, Streptomycin 100 ug/ml (complete medium). Keep tube on ice until biopsies are collected.
2. The core sample needs to be immediately placed into the complete medium and placed on ice and shipped to WCM using frozen ice packs on the same day of collection. ***Please do not freeze the samples.***

## APPENDIX 3 GI Toxicity Management Algorithm

## GI Adverse Event Management Algorithm

Rule out non-inflammatory causes. If non-inflammatory cause is identified, treat accordingly and continue I-O therapy. Opiates/narcotics may mask symptoms of perforation. Infliximab should not be used in cases of perforation or sepsis.

[figure not shown]
Patients on IV steroids may be switched to an equivalent dose of oral corticosteroids (e.g. prednisone) at start of tapering or earlier, once sustained clinical improvement is observed. Lower bioavailability of oral corticosteroids should be taken into account when switching to the equivalent dose of oral corticosteroids.

Updated 05-Jul-2016

## APPENDIX 4 Hepatotoxicity Management Algorithm

## Hepatic Adverse Event Management Algorithm

Rule out non-inflammatory causes. If non-inflammatory cause, treat accordingly and continue I-O therapy. Consider imaging for obstruction.

Patients on IV steroids may be switched to an equivalent dose of oral corticosteroids (e.g. prednisone) at start of tapering or earlier, once sustained clinical improvement is observed. Lower bioavailability of oral corticosteroids should be taken into account when switching to the equivalent dose of oral corticosteroids.

\*I-O therapy may be delayed rather than discontinued if AST/ALT  $\leq$  8 x ULN or T.bili  $\leq$  5 x ULN.

[figure not shown]
\*\*The recommended starting dose for grade 4 hepatitis is 2 mg/kg/day methylprednisolone IV.

Updated 05-Jul-2016

**APPENDIX 5: Skin Toxicity Management Algorithm**

**Skin Adverse Event Management Algorithm**

Rule out non-inflammatory causes. If non-inflammatory cause, treat accordingly and continue I-O therapy.

Patients on IV steroids may be switched to an equivalent dose of oral corticosteroids (e.g. prednisone) at start of tapering or earlier, once sustained clinical improvement is observed. Lower bioavailability of oral corticosteroids should be taken into account when switching to the equivalent dose of oral corticosteroids.

\*Refer to NCI CTCAE v4 for term-specific grading criteria.

[figure not shown]
^If SJS/TEN is suspected, withhold I-O therapy and refer patient for specialized care for assessment and treatment. If SJS or TEN is diagnosed, permanently discontinue I-O therapy.

Updated 05-Jul-2016

## APPENDIX 6: Endocrinopathy Management Algorithm

## Endocrinopathy Management Algorithm

Rule out non-inflammatory causes. If non-inflammatory cause, treat accordingly and continue I-O therapy. Consider visual field testing, endocrinology consultation, and imaging.

[figure not shown]
Patients on IV steroids may be switched to an equivalent dose of oral corticosteroids (e.g. prednisone) at start of tapering or earlier, once sustained clinical improvement is observed. Lower bioavailability of oral corticosteroids should be taken into account when switching to the equivalent dose of oral corticosteroids.

Updated 05-Jul-2016

## APPENDIX 7: Neurological Toxicity Management Algorithm

**Neurological Adverse Event Management Algorithm**

Rule out non-inflammatory causes. If non-inflammatory cause, treat accordingly and continue I-O therapy.

[figure not shown]
Patients on IV steroids may be switched to an equivalent dose of oral corticosteroids (e.g. prednisone) at start of tapering or earlier, once sustained clinical improvement is observed. Lower bioavailability of oral corticosteroids should be taken into account when switching to the equivalent dose of oral corticosteroids.

Updated 05-Jul-2016

## APPENDIX 8: Renal Toxicity Management Algorithm

## Renal Adverse Event Management Algorithm

Rule out non-inflammatory causes. If non-inflammatory cause, treat accordingly and continue I-O therapy

[figure not shown]
Patients on IV steroids may be switched to an equivalent dose of oral corticosteroids (e.g. prednisone) at start of tapering or earlier, once sustained clinical improvement is observed. Lower bioavailability of oral corticosteroids should be taken into account when switching to the equivalent dose of oral corticosteroids.

Updated 05-Jul-2016

## APPENDIX 9: Pulmonary Toxicity Management Algorithm

## Pulmonary Adverse Event Management Algorithm

Rule out non-inflammatory causes. If non-inflammatory cause, treat accordingly and continue I-O therapy. Evaluate with imaging and pulmonary consultation.

Patients on IV steroids may be switched to an equivalent dose of oral corticosteroids (e.g. prednisone) at start of tapering or earlier, once sustained clinical improvement is observed. Lower bioavailability of oral corticosteroids should be taken into account when switching to the equivalent dose of oral corticosteroids.

Updated 05-Jul-2016

## APPENDIX 10 Abbreviations

Abbreviation	Term
ADCC	Antibody Dependent Cellular Cytotoxicity
AE	Adverse Event
AEC	Absolute Neutrophil Count
ALC	Absolute Lymphocyte Count
ANC	Absolute Neutrophil Count
APC	Antigen Presenting Cell
BED	Biologically Effective Dose
BMS	Bristol-Myers Squibb
CBC	Complete Blood Count
CBCT	Cone-Beam CT
CDC	Complement Dependent Cytotoxicity
CDR3	Complementarity Determining Region 3
CR	Complete Response
CT	Computed Tomography
CTCAE	Common Terminology Criteria for Adverse Events
CTL	Cytotoxic T-Lymphocyte
CTV	Clinical Target Volume
DRR	Digitally Reconstructed Radiograph
DVH	Dose-Volume Histogram
irPFS	Immune-Related Progression Free Survival
irPR	Immune-Related Partial Response
irRC	Immune-Related Response Criteria
irSD	Immune-Related Stable Disease
irSPD	Immune-Related Sum of the Products of Diameters
IT	Immunotherapy
mAb	Monoclonal Antibody
MDSC	Myeloid-Derived Suppressor Cell
MLC	Multi-Leaf Collimator
MRI	Magnetic Resonance Imaging
NK	Natural Killer

Protocol version 6.0 dated 15JAN2020

Abbreviation	Term
MRI	Magnetic Resonance Imaging
NK	Natural Killer
NSAID	Non-Steroidal Anti-Inflammatory Drug
NSCLC	Non-Small Cell Lung Cancer
OLP	Overlapping Peptide
PBMC	Peripheral Blood Mononuclear Cell
PD	Progressive Disease
PD1	Programmed Death Receptor 1
PFS	Progression Free Survival
PR	Partial Response
PTV	Planning Target Volume
RCOIC	Research Conflict of Interest Committee
RECIST	Response Evaluation Criteria In Solid Tumors
RT	Radiotherapy or Radiation Therapy
RT-Ipi	Radiotherapy and Ipilimumab
SAE	Serious Adverse Event
SD	Standard Deviation
sMICA	Soluble MICA
SPD	Sum of the Products of Diameters
TA	Tumor Assessment
TAA	Tumor-Associated Antigen
TCR	T-Cell Receptor
TIL	Tumor Infiltrating Lymphocyte
TNM Staging	Tumor, Node and Metastasis Staging
WOCBP	Women of Child Bearing Potential

